 5.2 Intervention Training and Supervision11

6.0 SAFETY MONITORING PLAN12

 6.1 Data and Safety Monitoring Board.....12

Abbreviations:

TRB – Transmission Risk Behavior
MSM – Men who have Sex with Men
YMSM – Young Men who have Sex with Men
TLFB – Time Line Follow Back
STI – Sexual Transmitted Infection
BL – Baseline appointment
FU – Follow Up appointment

STUDY ABSTRACT

DESIGN: This study utilizes qualitative methods during a formative phase to inform intervention development. Subsequently a small randomized controlled trial is utilized in Phase 2 to evaluate the feasibility, acceptability, and preliminary efficacy of the new intervention relative to an attention-matched education control condition.

SAMPLE SIZE: In Phase 2 we will recruit a sample of 50 couples (n = 100 individuals). At least one member of the couple must be a YMSM between the ages of 18 and 29; report recent (past 30 days) drug use; and recent (past 30 day) Transmission Risk Behavior (TRB).

POPULATION: Partnered MSM aged 18-29 who are in a primary relationship with another man for at least 3 months, who also uses some kind of illicit drug, and also had some TRB in the last 30 days with a casual partner or with a non-monogamous serodiscordant partner. In addition all participants will have to be able to communicate in English.

STRATIFICATION: Participants will be randomized at baseline to receive their first CHP or Education session directly following their baseline appointment. The study will employ a stratified randomization procedure using Qualtrics.

DATA COLLECTION: Participants have the options to first complete a brief CASI at home before or during their BL appointment. Regardless, they will then complete another survey at their BL appointment along with a TLFB, STI testing (Gonorrhea & Chlamydia Urethral and Rectal), and Drug testing. During session 3, participants will complete a CHTC session that involves Rapid HIV testing for couples. For 1m FU participants will complete an at home Qualtrics survey. At 3M FU participants will complete a Qualtrics survey, a TLFB and a Fingernail specimen collection for drug use.

[figure not shown]
Study Procedure Guide (SPG)

Finally, at 6M FU participants will complete a Qualtrics survey, a TLFB and Specimen collection to test drug use on fingernail sample and Gonorrhea & Chlamydia for STI testing (Urethral and Rectal).

OBJECTIVES

- 1) Develop content to address PrEP uptake/adherence and integrate biological testing
- 2) Evaluate the efficacy, feasibility, and acceptability of CHP at 3- and 6-month follow-up.

STUDY DESIGN:

Original Study Timeline:

Month	Year 1					Year 2		Year 3	
	1-2	3-4	5-8	9	10-12	13-18	19-24	25-30	31-36
Planned activity									
Phase I: intervention development									
Startup	■								
Interviews with partnered YMSM (n = 20)		■							
Qualitative data analysis			■						
Intervention development and staff training				■					
Phase II: enrollment									
Enrollment (n = 50 couples; 100 individuals)						■	■	■	■
Follow up data collection						■	■	■	■
Data analysis									
Dissemination of qualitative findings						■			
Intervention outcome analyses									■

STUDY POPULATION

3.1 Inclusion and Exclusion Criteria

a. Inclusion

- i. One partner must be 18 to 29 years of age
- ii. Both partners born male and currently identify as male
- iii. One partner must be HIV-negative (one partner can be HIV positive)
- iv. In a relationship with another man for at least 3 months
- v. Either partner reporting the use of at least one of the following substances in the past 30 days Marijuana, cocaine and crack, amphetamines, ecstasy, GHB, ketamine, nitrates
- vi. Either partner reporting CAS with a casual partner and/or CAS with a non-monogamous or serodiscordant main partner in past 30 days.
- vii. Must be able to communicate English
- viii. Must reside in the NYC metro area

b. Exclusion

- i. Either member of the couple reports IPV, which is defined as serious physical or sexual violence that occurs outside the context of consensual bondage or sado-masochistic sexual play, which results in concerns of safety (IPV-GBM scale)
- ii. Unstable, serious psychiatric symptoms
- iii. Currently suicidal/homicidal
- iv. Evidence of gross cognitive impairment

3.2 Recruitment and Screening

This study will utilize an index case approach for the recruitment of couples in which one partner will be screened. Those providing data that indicate they are eligible will then be asked to schedule a baseline appointment during a timeslot on a day that they can attend with their partner. This strategy has proven effective in our previous studies of gay couples, substantially more effective than procedures that require advanced screening of both partners. The study will utilize active and passive approaches to recruit index participants.

3.3 Contact Information

Once they are screened eligible through our online screener participants contact information will be collected and they will be asked if messages can be left at the numbers provided or if text can be sent. Study staff will not leave messages or send text messages unless expressly permitted to do so by the participant, which also will be documented on the participant Locator Form and Access DB.

4.0 STUDY PROCEDURES

4.1 At-home CASI

Once participants schedule their baseline appointment, they will be sent an appointment reminder email with instructions to find PRIDE's office and the time of the appointment. This email will contain a link to a Qualtrics survey for them to complete prior to the baseline appointment. The index partner (participant 1) will be sent two emails: one will contain their unique Qualtrics survey link and a second email to be forwarded to their partner (participant 2) so they can access their Qualtrics survey link. When participant 2 completes the at-home CASI they will be asked to leave contact information.

In the unlikely event that either participant in the couple answers "yes" to the question about IPV or coercion, both members of the couple will be ineligible for the study. In this scenario, each participant will be compensated \$10 for completing the at-home CASI via Amazon gift card.

If participants do not complete this CASI prior to their baseline appointment, they will have to complete it in the office the day of their baseline.

4.2 Enrollment Procedures

Participants are considered enrolled in the study databases when they have completed informed consent in person.

4.2.1 Informed Consent Process

Details of the study will be reviewed with the prospective study participant by a designated site study staff member trained and cleared to conduct assessments and is knowledgeable about the research study. This discussion is a critical component of the consent process and the prospective study participant will be given adequate time for this discussion and to read the written consent form. The Principal Investigator (PI) or his/her designee will be available to answer questions about the study including participant responsibilities, benefits, risks, and alternatives. A shortened version of the consent form will be delivered electronically to the participant prior to beginning participation in the study, and then the full consent form will be reviewed at the

beginning of the in-person baseline appointment. The participant will review the consent form and it will be signed and dated by both the participant and study staff member conducting the assessment. A copy of the signed consent form will be given to the participant and the original will be kept securely by the project coordinator separate from other assessment materials.

4.3 Randomization Process/Systems

Participants will be randomized at the end of their baseline assessment into one of two control conditions: 1) delivery of the 3 session CHP intervention or 2) delivery of a 3 education sessions. Each participant's condition will be tracked in the access tracking database maintained by the Research Coordinator.

The study will employ a stratified randomization procedure for each interventionist using Qualtrics. Randomization will be stratified on:

1. Age discrepancy Question: is the couples age difference (3 years or less/ longer than 3 years)
2. Relationship Length Question: is the couple's relationship length (2 years or less/longer than 2 years)
3. Racial makeup question: is the couples racial makeup (both partners identify as white and non-Hispanic/one or both partners identify as nonwhite or Hispanic)

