5.0 CHP INTERVENTION/EDUCATION PROCEDURES

5.1 Intervention Design and Procedures

CHP is an intervention that utilizes motivational interviewing (MI) and personalized feedback to reduce CAS and substance use among partnered emerging adults. The CHP intervention will be delivered by MI-trained Clinical staff members. Participants will be randomized to receive the intervention during baseline appointment. The CHP intervention is comprised of 3 sessions. The intervention focuses on enhancing communication skills, and addressing drug use, risky sexual practices, couples HIV testing and counseling, PrEP and PEP, as well as navigation services to for PrEP for interested participants.

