5.3 Sessions Training and Supervision

CHP Sessions training will occur prior to the initiation of Phase 2, with ongoing coaching, supervision and training of new therapists as well as educators, as required. The training manuals are located on appendix B for Intervention & CHTC and Appendix C for Educators.

Training for CHTC entails going through a series of trainings as well as mock sessions in order to get “Cleared” by clinical staff to conduct CHTC with participants. The same procedure will be followed for Educators, but they will be evaluated in their ability to present the education information and how to engage with the participant while avoiding the use of MI techniques.

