Couples Health Project: Data Analysis Plan

Development of a couples-based intervention to reduce drug use and enhance sexual health among partnered emerging adults.

NCT# 03386110 LAST UPDATED: 6/1/2021

Analytic plan

A series of bivariate analyses conducted using the generalized estimating equations function within SPSS (version 25) evaluated the success of randomization and the presence of differential attrition. In models evaluating randomization, condition (MI-intervention versus control) served as the sole predictor of baseline characteristics. Analogous models evaluating differential attrition predicted baseline characteristics from a dichotomous variable indicating whether or not a participant completed a specific follow-up.

Multi-level models calculated in Mplus (version 8.2; 48) evaluated primary hypothesized direct treatment effects. These models controlled for the nesting of participants within couples and permitted the specification of logistic and count (Poisson or negative-binomial) distributions as appropriate. Full-information maximum likelihood estimation was utilized to retain all cases in a true intent-to-treat paradigm. For each outcome, 3- and 6-month values were predicted by treatment condition.

The hypothesis that baseline frequency of drug use or CAS with casual partners may moderate the effects of treatment was evaluated using the Actor-Partner Interdependence Model (APIM) framework (49). Models incorporated participants' own baseline report of the outcome (actor scores) as well as their partners' report (partner scores) at Level 1. Interactions among actor and partner baseline scores and treatment condition were also included at Level 1. This included the 3-way interaction term as well as all possible 2-way interactions. A natural log transformation was used to address skew in these predictor variables. For models involving count-distributed outcomes, effect size was calculated using procedures outlined by Larsen and Merlo (50) for the calculation of an Interval Odds Ratio.

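### The SAP outcome models leave out the three factors used to stratify randomisation, and the protocol's per-interventionist wording needs explaining

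*Protocol*

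**What the plan says.** **Randomisation.** Protocol section 4.3 provides for a "stratified randomization procedure for each interventionist using Qualtrics". It then lists three stratification factors, each with two levels:

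- age gap within the couple, split at three years;
- length of the relationship, split at two years;
- racial makeup, contrasting couples in which both men are white and non-Hispanic with all others.

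Interventionist is not in that list. The Study Abstract describes the same procedure without it: "The study will employ a stratified randomization procedure using Qualtrics". Neither place gives the block size, the number of interventionists, or when a couple is linked to one.

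**Staff.** Section 5.1 says: "The CHP intervention will be delivered by MI-trained Clinical staff members". Section 5.3 says educators are judged on how they "engage with the participant while avoiding the use of MI techniques". Section 4.6 refers to a participant's assigned clinician or educator, according to condition.

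**Analysis.** On the primary models the SAP says: "These models controlled for the nesting of participants within couples". The 3- and 6-month values of each outcome are predicted from condition. The moderation models add the participant's own and the partner's baseline score, with their interactions with condition. No model contains a stratification factor or the interventionist.

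**The concern.** Stratified allocation makes the arms alike on the chosen factors, so differences between strata add little to the true variance of the treatment contrast. A model without the factors still counts those differences as residual noise. Its standard error is then larger than it should be, intervals are too wide, and the precision that stratification was meant to secure is lost. With 50 couples and an aim that includes preliminary efficacy, there is little precision to spare.

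The wording about interventionists is a separate, smaller matter. If CHP staff and educators are different people, the interventionist is known only once the arm is known. Arms then cannot be allocated within interventionist, and a reader cannot tell what was done. If each staff member saw several couples in one arm only, outcomes may also cluster by staff member, which the models do not allow for.

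**Working it through.** **1. The plan's own figure.** 50 couples × 2 = 100 individuals, which agrees with the Study Abstract. The documents give no alpha, power, effect size or intraclass correlation (ICC), so the sample size cannot be re-derived further. I assume 1:1 allocation of couples and a two-sided 5% test.

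**2. Design against analysis.**

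| Element | Protocol 4.3 | SAP models |
|---|---|---|
| Age difference | stratified | absent |
| Relationship length | stratified | absent |
| Racial makeup | stratified | absent |
| Couple | level at which the factors are defined | nesting modelled |

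The three factors give 2 × 2 × 2 = 8 cells, or 50 / 8 = 6.25 couples per cell. That is workable.

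**3. Effect of leaving the factors out.** Let R² be the share of couple-level outcome variance that the factors explain. With near-complete balance, the true standard error is about √(1 − R²) times the one reported, so the actual size of a nominal 5% test is 2 × [1 − Φ(1.96 / √(1 − R²))]. The documents do not give R², so I show a range.

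| Assumed R² | √(1 − R²) | 1.96 / √(1 − R²) | Actual size |
|---|---|---|---|
| 0.05 | 0.975 | 2.011 | 4.4% |
| 0.10 | 0.949 | 2.066 | 3.9% |
| 0.20 | 0.894 | 2.191 | 2.8% |
| 0.30 | 0.837 | 2.343 | 1.9% |

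At R² = 0 the size stays at 5%. The formula is for a linear model. The SAP also uses logistic and count models, for which it shows direction and rough size only.

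**4. Cost of adjusting.** A two-arm comparison of 50 couples leaves 50 − 2 = 48 couple-level degrees of freedom. Three binary covariates leave 45.

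**5. The interventionist wording.** Section 4.3 randomises by interventionist, while the Study Abstract does not mention it. Sections 4.6, 5.1 and 5.3 describe staff by arm. The passages fit together only if couples were linked beforehand to a clinician–educator pair, if staff delivered both conditions, or if the phrase is loose wording. None of these is stated.

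**6. Why a staff-level sensitivity analysis is worth having if staff were nested in arm.** With m = 25 / (staff per arm) couples each, the design effect is DE = 1 + (m − 1) × ICC and the size is 2 × [1 − Φ(1.96 / √DE)]. Staff numbers and ICC are assumptions.

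| Staff per arm | m | Size at ICC 0.01 | Size at ICC 0.05 |
|---|---|---|---|
| 2 | 12.5 | 6.3% | 11.8% |
| 3 | 8.33 | 5.9% | 9.4% |
| 4 | 6.25 | 5.6% | 8.1% |

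These figures apply the same ICC to both arms. If only CHP clusters by staff, the average design effect is (1 + DE) / 2, and ICC 0.05 gives about 8.4% (two staff) to 6.5% (four).

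**The case against.** The best defence is that omitting strata is a conservative error. It costs power but creates no false positives, and it does nothing if the factors are not prognostic. The trial is small and described as testing feasibility, acceptability and preliminary efficacy. In logistic models, adjustment changes the odds ratio being estimated and need not shrink its standard error. All of this stands, and it limits the size of the point. It does not explain leaving out factors that the design treated as important and that had to be recorded in order to randomise.

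A reader might go further in three ways that the documents do not support.

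- **That stratifying by interventionist split 50 couples too finely.** Interventionist is not among the three listed factors, and the number of staff and the block size are not given. The extra cells could exist only if staff were fixed before allocation. Even with four interventionists and blocks of 4, both assumed, the simulated mean gap in arm size is 4.0 couples. It is 2.0 with the eight cells alone and 5.6 with simple randomisation, so the balance is still better than with no stratification.
- **That the standard errors are shown to be wrong in both directions.** The conservative effect follows from the text to the extent that the factors are prognostic. The opposing effect needs staff nested in arm, a staff count and a staff ICC. The first is only inferred from role descriptions, and the other two are not given.
- **That staff crossed with arm would have defeated the separation of MI from education.** Educators are assessed on avoiding MI (section 5.3), and at least 30% of completed education sessions were reviewed for fidelity (section 5.5).

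**Conclusion.** The main point holds: the design stratifies on three couple-level factors and no outcome model in the SAP includes them. The consequence is lost precision. A nominal 5% test runs at about 4.4% to 1.9% if the factors explain 5% to 30% of couple-level variance, with no loss if they explain none. This rests on an assumed R², near-complete balance and a linear approximation.

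The secondary point is one of clarity. The per-interventionist wording does not fit the staff roles described elsewhere and is missing from the Study Abstract. It does not show that the randomisation was faulty. Staff clustering is a possibility to check, not a demonstrated error.

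**What to change.** 1. **Adjust for the strata.** Enter the three binary factors as couple-level covariates in every SAP outcome model, both the direct-effect and the moderation models. Randomisation required their values, so they should be available for every randomised couple. The SAP is dated 6/1/2021 and written in the past tense, so show the unadjusted results alongside and identify the adjusted ones as added. The cost is three degrees of freedom with 50 couples and, in logistic models, an odds ratio conditional on the factors rather than marginal over them.

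2. **State what was done.** Reconcile section 4.3 with the Study Abstract and with sections 4.6, 5.1 and 5.3. Say what randomising for each interventionist meant, how many interventionists there were, whether any delivered both conditions, what block size was used, and that the couple was the randomised unit, if so. The SAP's tense and the notes on remote follow-up after 3/15/2020 suggest that allocation is complete. Simply deleting the phrase could therefore misreport the procedure. This costs a few sentences.

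3. **If staff were nested in arm**, report one sensitivity analysis that allows for interventionist clustering, and note that its variance estimate will be imprecise with few staff. It should not replace the primary analysis.

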4.4 Schedule of Assessments

Intervention or education sessions will occur approximately once per week for two weeks beginning one week after completion of the baseline assessment and session 1. There is a 6 week window (45 days) for intervention or education completion, i.e. opportunities to complete all three sessions must be provided before the 1 month online follow up survey is sent out.

Participants will complete the first follow-up assessment online 1 month after baseline (1M FU). For those who have completed all sessions by day 30 post BL, they will be sent their 1 month follow up survey. For those who have yet to complete all 3 sessions they will be given until day 45 post baseline until their session window closes and they must be sent their 1 month follow up survey. The 1 month follow up survey will close 60 days post baseline. Follow up assessment windows for 3 month and 6 month follow ups will be programmed to open on day 90 and day 180 respectively and will remain open for 30 days.

Component	Screening	Baseline	Session 1	Session 2	Session 3	Booster	1-Month Follow-Up	3-Month Follow-Up	6-Month Follow-Up
Informed Consent		X							
CASI		X					X	X	X
HIV Testing					X				
STI Testing (G&C)		X							X
Fingernail Drug Test		X						X	X
Randomization		X							
Randomized Condition Session			X	X	X	X			
TLFB		X						X	X
Assessment of Intervention feedback					X				
Assessment of Intervention feedback (If not completed or captured in session 3)							X		

Refer to “Study Design” for a visual representation of the schedule of assessments.

4.5 Managing and Tracking Study Visits

There are two different types of visits during the study timeline:

Intervention/Education Sessions: All CHP sessions will be managed by trained staff members. Therapists and Educators will notify the project coordinator whether visits were completed for tracking purposes, provide receipt for session compensation and audio files will be uploaded to the designated secure location on PRIDE servers. Session 1 for CHP or Education session will ideally begin directly after the completion of the baseline appointment when feasible. Otherwise it will be scheduled for a later date. Randomization to CHP or education will occur during the baseline appointment.

Research Appointments: Research visits include the baseline visit, 3 sessions, and all other follow-up assessments.

Research visits will be tracked using Access Database, encrypted and secure on a private server at PRIDE offices, as well as Qualtrics which is a secure web application for managing online surveys. This system allows study staff to monitor the completion of study visits and surveys, and generate reports on enrollment and retention as needed. Study staff is expected to track all completed study components in Access immediately after completing an assessment and no later than end of business day.

Study staff will schedule participants during times that they will be available or will contact other staff to ensure coverage for appointments. Study staff will also ensure that there is available space to conduct these assessments.

Future visits should be scheduled during the study visit. Study staff is expected to keep in touch with participants and remind them of the upcoming visit or reschedule if needed. A reminder call should be made the day before a participant is due to come in for their visit (or the Friday before a Monday visit).

